7. STUDY OUTCOMES

The primary outcomes of interest are:

- Re-operation (revision, incision, excision, removal) or mesh removal
- Chronic pain, defined as pain persisting at least three months after surgery⁴⁹
- Voiding symptoms, defined as recurrence of incontinence or new retention.

All outcomes are determined in the surveillance period after surgery. Re-operation or mesh removal is defined as a surgery for any kind of mid-urethral sling, urethral bulking agent, bladder neck pubovaginal sling (autologous or allograft), or revision for mesh exposure. Resumption of voiding symptoms was defined as subsequent urinary retention, urinary incontinence, and sling revision for urinary retention. Chronic pain is defined as a new post-operative pain score >3 of 10 on vital sign data occurring over at least 3 months or greater of duration, or diagnosis codes related to abdominal and pelvic pain.

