Outcome	Re-Operation	 CPT code based Reoperation for Mesh Revision/Removal sling revision/removal-CPT codes 57287, 10120 Removal of Autologous Tissue Substitute from Urethra, Open Approach (ICD 10 PCS 0TPD07Z). Removal of Synthetic Substitute from Urethra, Open Approach (ICD 10 PCS 0TPD0JZ). Removal of Nonautologous Tissue Substitute from Urethra, Open Approach (ICD 10 PCS 0TPD0JZ). Revision of Autologous Tissue Substitute in Urethra, Open Approach (ICD 10 PCS 0TWD07Z). Revision of Autologous Tissue Substitute in Urethra, Open Approach (ICD 10 PCS 0TWD07Z). Revision of Synthetic Substitute in Urethra, Open Approach (ICD 10 PCS 0TWD07Z). Revision of Nonautologous Tissue Substitute in Urethra, Open Approach (ICD 10 PCS 0TWD07Z). Revision of Nonautologous Tissue Substitute in Urethra, Open Approach (ICD 10 PCS 0TWD0Z). Revision of Nonautologous Tissue Substitute in Urethra, Open Approach (ICD 10 PCS 0TWD0KZ). Reoperation for Mesh Revision/Removal Subtypes: Hemorrhage/bleeding (ICD9/10 459.0, 998.11, 623.8 or 596.89/ R58, N99.820, N99.821) Nerve injury (ICD9/10 956.3, 956.5, 956.8, 956.9, 957.9/S30-S39, S84.10XA, S74.8X9A) Pain (ICD9/10 338,338.1,338.2, 338.21, 	Yes	revision, incision, excision, removal. Represented as a Date, allows time-to-event analysis. Some of the covariate & outcome variables pertaining to degree of recurrence (may not be ascertainable in structured data, will require text search), including urinary urgency as a symptom (depends on the pre-operative visit, under-documented in structured data)

Protocol 1		1		[15 July 2020]

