		 Mesh exposure and erosion (ICD9/10 629.31, 629.32/T83.711, T83.721) Urinary Retention (CPT Code 53500, ICD 9/10 788.20, 788.21/R33.0, R33.8-R33.9) Urgency of urination (ICD9/10 788.63/R39.15) Urge incontinence (ICD9/10 788.31/N39.41) Bowel injury (ICD9/10 569.83/S36) Bladder/urethral injury (ICD9/10 596.6,867.0/S37) Infection (ICD9/10 686.9,998.5,999.3,998.51,998.59/T81) Retropubic hematoma (ICD 9/10 568.81,,568.81,459.0/K66.1) Retopubic hematoma (ICD 9/10 568.81,,568.81,459.0/K66.1) Retopubic hematoma (ICD 9/10 568.81,568.81,459.0/K66.1) Bulking Injection CPT 51715, ICD 9/10 59.72/ PCS 3E0K3GC Laparoscopic Retropubic Urethropexy CPT 51990, 51992, 51999 Abdominal Retropubic Urethropexy CPT 51840,51841 Needle Bladder Neck Suspension CPT 51845 Kelly plication CPT 57220 Cystourethroplasty CPT 51800 Subtypes: Stress incontinence, female/mixed incontinence (ICD9/10 625.6,788.33/N39.46) Stress incontinence (female) (male)(ICD10 CM N39.3) 		
Outcome	Mesh Removal	 General, CPT 57287-Removal or revision of sling for stress incontinence (fascia or synthetic) ***some erosions managed surgically may have been coded by a different CPT (i.e. 57295 revise vaginal graft via vaginal approach) and not CPT 57287, which indicates a sling revision/removal. 	Yes	Possible Options: (a surgery for any kind of mid-urethral sling, urethral bulking agent, black neck pubovaginal sling (autologous or allograft), or revision for mesh exposure). Represented as a Date, allows time-to-event analysis.
Outcome	Post-Procedural Pain	?, mix of vital sign (pain score >3 of 10 on vital sign data) and likely free text. Also, diagnosis codes related to abd/pelvic pain (if prior pain free).	Some portion	Would have to exclude prior chronic pain or detect specific mention of new pain (free text). Could analyze group with no pre-surgical pain,

Protocol 1				[15 July 2020]
				otherwise probably beyond scope. Date/Time of first post- op occurrence.

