Outcome	Mesh Erosion	Admin Codes: ICD-9-CM codes for mesh erosion: 996.30, 996.39, 996.59, 996.60, 996.65, 996.69, 996.70, 996.76, 996.79, 939.0, 939.2, and 939.9 ICD 10 CM: T83.498A, T85.698A, T85.79XA, T83.598A, T85.79XA, T85.9XXA, T83.89XA, T85.898A, T19.0XXA, T19.2XXA, T19.9XXA Surgical Complications: ICD 9/10 629.31/T83.711 Erosion of implanted vaginal mesh ICD 9/10 629.32/T83.721S Exposure of implanted vaginal mesh ICD 9/10 996.76/T83.9 Complication of genitourinary device, implant or graft ICD9/10-PCS V58.2/30233N1, 30233P1, 30233H1 Blood transfusion ICD9/10 998.5/ T81.49XA, T81.40XS, T81.41, T81.43, T83.5, T83.6 Postoperative infection ICD 9/10 778.2/R33.9 Urinary retention		Capture as date/time Exclude 629.3- complication of implanted vaginal mesh and other prosthetic materials, 629.31- erosion of implanted vaginal mesh, or 629.32-exposure of implanted vaginal mesh because these ICD-9 were not released until 2011? ²⁸ SME determined that topical estrogen could be prescribed for other reasons
Outcome	Urethral fistula	Admin Codes ICD 9- 599.1 ICD 10-N36.0	Yes	Capture as date/time
Covariate	Prior Abdominal Surgery Or Pelvic Radiation	Admin Codes: Personal history of irradiation-V15.3/Z92.3, Irradiation cystitis- N30.4	Yes	Yes/No
	Therapy	CPT/ICD 9/ICD 10 for prior abdominal surgery:		

Protocol 1		[15 July 2020]
	Hysterectomy: 00846, 00855, 00944, 01962,	
	01963, 01969,45126, 51597, 51925, 56308,	
	58150, 58152, 58180, 58200, 58205, 58210,	
	58240, 58260, 58262, 58263, 58265, 58267,	
	58270, 58275, 58280,	
	58285, 58290, 58291, 58292, 58293,	
	58294, 58541, 58542, 58543, 58544,	
	58548, 58550, 58552, 58553, 58554,	
	58570, 58571, 58572, 58573, 58575,	
	58951, 58953, 58954, 59135,	
	59525, 59560, 59561, 59580, 59581	
	/68.9/290.711	
	Cesarean section: 00850, 59500, 59501,	
	59520, 59521, 59540, 59541/649.81/075.82	
	Appendectomy: 44950, 44955, 44960,	
	44970, 49315, 56315/V45.79/Z90.89	
	Hernia repair: 49505, 49507, 49520,	
	49521, 49525, 49550, 49553, 49555,	
	49557, 49560, 49561, 49565, 49566,	
	49570, 49572, 49585, 49587, 49590,	
	49650, 49651, 49652, 49653, 49654,	
	49655, 49656, 49657, 49659/53.5/0WQF0ZZ,	
	0WQF3ZZ, 0WQF4ZZ	
	Cholecystectomy: 47562, 47563, 47564, 47600,	
	47605, 47610, 47612, 47620/51.0-	
	51.04/0FT40ZZ	
	51.04/01 14022	
	Colectomy: 44139, 44140, 44204, 44205, 44206,	
	44141, 44143, 44144, 44145, 44146, 44147,	
	44150, 44151, 44157, 44158, 44160,44320,	
	44322, 44799, 45110, 45111, 45112, 45113,	

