	45114, 45119, 45120, 45121, 45123, 44204,	
	44205, 44206, 442Ø7, 442Ø8, 4421Ø, 44211,	
	44212, 44213, 44238, 45395, 45397/45.8, 45.81,	
	45.82, 45.83/0DTE4ZZ, 0DTE0ZZ, 0DTE7ZZ,	
	ODTE8ZZ	
	Lysis of abdominal adhesions: 44108, 44005,	
	58660, 58740, 53500/ 54.5, 54.51,	
	54.59/0DN84ZZ, 0DNE4ZZ, 0DNJ4ZZ, 0DNU4ZZ,	
	ODNV4ZZ, ODNW4ZZ, OFN04ZZ, OFN44ZZ,	
	OFN48ZZ OFN54ZZ, OFN64ZZ, OFN74ZZ, OFN84ZZ,	
	OFN94ZZ, OFNG8ZZ	
	Oophorectomy- 58661, 49321-51,	
	58940/V45.77/ Z90.722, Z90.721	
	555 10, 145.11, 250.122, 250.121	
	Cystocele and rectocele repair- 57260-51, 57282,	
	57267, 57270, 61809, 57240/70.50/ 0JQC0ZZ,	
	0JQC3ZZ	

Protocol 1			•	[15 July 2020]
		Gastrectomy- 43631, 43632, 43633,		
		43634/V45.75/Z90.3		
		Hystorestemy ⁵⁴ abdominal and vaginal		
		Hysterectomy ⁵⁴ , abdominal and vaginal C section		
		Appendectomy		
		Hernia repair		
		Cholecystectomy		
		Colectomy or colorectal resection		
		Excision, lysis peritoneal adhesions		
		Oophorectomy, unilateral and bilateral		
		Repair of cystocele and rectocele, obliteration of		
		vaginal vault		
		Gastrectomy		
		Other		
Outcome	Surgical Site Infection	Admin Codes & Free Text	Partially	Capture as date/time
		Pelvic, perineal abscess, or infection due to		Lahey Question:
		internal prosthetic device, implant and graft		Can antibiotic use in
		Infection due to implant:		within X days be a proxy
		996.69/T85.79XA		for SSI?
		Pelvic abscess ICD9/10:567.22/K65.1		
		614.3/N73.0		
		614.9 or 616.9/N73.9		
		614.4/N73.1		
		614.5/N73.5, N73.3		
		014.5/10/5.5/10/5.5		
		Perineal abscess ICD9/10:		
Outcome	Organ Mesh	682.2/L02.215 Admin Codes & Free Text (Possibly)	Vec	Direct surgical
Outcome	Organ Mesh	Admin Codes & Free Text (Possibly)	Yes	Direct surgical
Outcome	Perforation	Admin Codes & Free Text (Possibly) • Erosion of other implanted mesh to	Yes	complication, capture as
Outcome	Perforation (vagina, urinary	Admin Codes & Free Text (Possibly) • Erosion of other implanted mesh to organ or tissue ICD10CM-T83.712	Yes	_
Outcome	Perforation	Admin Codes & Free Text (Possibly) Erosion of other implanted mesh to organ or tissue ICD10CM-T83.712 Erosion of implanted urethral mesh to 	Yes	complication, capture as
Outcome	Perforation (vagina, urinary	 Admin Codes & Free Text (Possibly) Erosion of other implanted mesh to organ or tissue ICD10CM-T83.712 Erosion of implanted urethral mesh to surrounding organ or tissue, initial 	Yes	complication, capture as

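### CPT 53500 has two inconsistent meanings in the appendix and is missing from the codes that define re-operation and voiding events

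*Protocol*

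**What the plan says.** All the code lists are in the Data Collection table of Protocol Section 13.

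- **Re-Operation row, procedures.** The row is described as based on CPT codes. It opens with "sling revision/removal-CPT codes 57287, 10120" and a run of ICD-10-PCS removal and revision codes.
- **Re-Operation row, subtypes.** A second list follows, beginning "Reoperation for Mesh Revision/Removal Subtypes: Hemorrhage/bleeding". One of its items is "Urinary Retention (CPT Code 53500, ICD 9/10 788.20, 788.21/R33.0, R33.8-R33.9".
- **Prior abdominal surgery covariate.** Under "CPT/ICD 9/ICD 10 for prior abdominal surgery" stands the item "Lysis of abdominal adhesions: 44108, 44005", whose codes continue "58660, 58740, 53500/ 54.5, 54.51".
- **Mesh Removal row.** It gives 57287 and warns that some surgically managed erosions may carry another code, such as 57295. It does not mention 53500.
- **Voiding symptoms row.** It lists retention, incontinence and other diagnosis codes, and retention with catheterisation. It does not list 53500.

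Section 7 includes incision among the kinds of re-operation and makes "sling revision for urinary retention" part of the voiding outcome. Aim 2 in Section 3 covers voiding symptoms that are new or that lead to a further operation.

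**The concern.** CPT 53500 is a procedure code, yet in the Re-Operation row it stands among reasons for an operation and not among the operations. The same code then counts as abdominal adhesiolysis in a baseline covariate. The protocol gives no descriptor and no rule that would let both uses stand.

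Re-operation and voiding symptoms are two of the three primary outcomes in Section 7. A woman who returns to theatre for retention and is coded 53500 could be missed by the first and, depending on her diagnosis codes, by the second. If she is later coded 57287, she is counted but dated late, which matters in a time-to-event analysis. Under Section 6 one site writes the transformation code for all sites, so one reading of the list applies everywhere.

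**Working it through.** No sample size or rate is involved, so the check compares the lists and then traces patients through them.

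**1. Where the code stands.** It occurs twice: as a retention subtype of re-operation, and as adhesiolysis before the index surgery. It is absent from the revision/removal procedures (57287, 10120, ICD-10-PCS), from the SUI procedures later in the same row (51715, 51990, 51992, 51999, 51840, 51841, 51845, 57220, 51800), from Mesh Removal and from Voiding symptoms.

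**2. Do subtypes define events or only classify them?** No rule is stated. Suppose any subtype code could define an event alone. Then a bare diagnosis of bleeding (R58), infection (T81) or urgency (R39.15) would be a re-operation, which cannot be meant. The natural reading is that a procedure code finds the event and the subtype gives its reason. In the retention item, 53500 is the only CPT code beside diagnosis codes.

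**3. Patients traced on that reading**, each with no listed code other than those shown:

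- *53500 with 57287:* a re-operation with reason retention, and a Mesh Removal event.
- *53500 with ICD-9 788.21:* not a re-operation; a voiding event through the diagnosis.
- *53500 with R33.9 and CPT 51701 or 51702:* not a re-operation; a voiding event.
- *53500 with R33.8 (or R33.0, or R33.9 without a catheterisation code):* no event in Re-Operation, Mesh Removal or Voiding symptoms. The Voiding row's main retention list holds ICD-9 codes only, although it is labelled for both versions.
- *53500 first, 57287 later:* a re-operation dated at the later procedure.
- *53500 before the index surgery:* recorded as prior abdominal surgery.

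The fourth case is realistic, because Section 4 says the study spans the ICD-9 and ICD-10 eras.

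**4. Against the stated outcomes.** Section 7 counts sling revision for retention and names incision as a form of re-operation; Aim 2 counts voiding symptoms that require re-operation. If 53500 denotes such an operation, the fourth case should be an event and is not.

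**5. Size.** Let *s* be the share of retention operations coded 53500 with no event-defining code. The reported retention re-operation rate is then (1 − *s*) × the true rate, so the relative shortfall is *s*. The documents give nothing from which *s* could be estimated.

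**The case against.** The strongest reply is that the code does sit inside a Re-Operation row described as CPT-based, and no sentence says a subtype cannot qualify. As the lone CPT code in that item, it could have been meant as a qualifying procedure. The list is also visibly disordered: the retropubic hematoma item is repeated, and the SUI procedures follow the revision subtypes with no clear heading. This stands as a reason not to claim certainty about the hierarchy. It does not remove the problem, because a programmer still cannot tell what to do with 53500, and the double use does not depend on layout.

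A reader might infer that operations coded 53500 are never counted, or that both primary outcomes miss them. The documents do not support that. A case also coded 57287 is a re-operation on any reading, and Section 7 counts retention itself as a voiding event, so a listed diagnosis code is enough there.

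A reader might also put a figure on the loss. An assumed share of 10 to 30% would turn a true 1.0% into 0.9 to 0.7% (1.0% × 0.90 and 1.0% × 0.70), but this only restates the assumption.

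Nor do the documents show which label is right, so unconditional deletion from the adhesiolysis list would go too far. Section 7's detailed definition of re-operation also does not name a stand-alone operation for retention, although its headline includes incision. That is a further point to reconcile, not a defence of the list.

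On the covariate side the harm is small: one code among dozens feeding a yes/no variable.

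Chart review of 50 to 100 cases per site is some protection, but a weak one. At a purely illustrative 1% frequency, and with charts chosen without regard to outcome, it would contain 50 × 0.01 = 0.5 to 100 × 0.01 = 1 such case per site.

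**Conclusion.** The point holds as an inconsistency in a code list that the protocol itself fixes. One code is given two meanings, and it is absent from every list of event-defining procedures. On the natural reading, an operation for retention coded 53500 without 57287, 10120 or a listed ICD-10-PCS code is not a Re-Operation event. It reaches the voiding outcome only through an accompanying listed retention or incontinence code, and ICD-10 coverage of retention there is thin.

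This rests on two assumptions: that subtypes classify and do not define events, and, for the conflict with Section 7 and Aim 2, that 53500 denotes an operation for retention. If it denotes adhesiolysis, the error is its place in the retention subtype. Either way the list needs correcting. The direction of any bias under the first meaning is towards too few or too late re-operations for retention; its size is unknown.

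**What to change.** Check the code's descriptor and give CPT 53500 one meaning throughout.

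- *If it is an operation for retention:* list it with the event-defining re-operation codes, with retention as the reason; add it to the part of the voiding outcome that covers sling revision for retention; and remove it from the adhesiolysis covariate.
- *If it is adhesiolysis:* remove it from the retention subtype.

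State in one sentence whether subtype codes can define an event or only classify one. Reconcile the Section 7 definitions with the Re-Operation, Mesh Removal, Voiding symptoms and Prior Abdominal Surgery rows before the shared transformation code is fixed. The cost is the placement of one code and one clarifying sentence, with no new data.

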However, by the mid-2000's, a growing number of adverse event reports had been submitted to the MAUDE FDA database related to trans-vaginal synthetic mesh products used for these indications. During 2005-2010, MAUDE received 1371 reports of injury, death, and malfunction of mesh for SUI treatment, related to mesh erosion, pain, infection, recurrence of urinary symptoms, and organ perforation, along with a 5-fold increase in MAUDE reporting rates in 2008-2010 compared to 2005-2007. While these numbers increased scrutiny surrounding these devices, a lack of denominator data and a reliance on voluntary reporting that is sensitive to FDA and press scrutiny limit the interpretability of these findings.

Risk assessments around synthetic surgical mesh for SUI remains uncertain for some outcomes extending beyond one year²⁵. [name] and colleagues evaluated a New York State prospective registry (SPARC) that included all surgeries and evaluated 41,604 women undergoing mesh implantation for pelvic organ prolapse or stress urinary incontinence. Among the 22,252 women undergoing surgery for SUI, 1.6% of them had mesh erosions that required intervention²². In one UK study, overall re-operation rates were only 3.2% among mid-urethral sling procedures for SUI after a median 2.8 years of follow-up²⁶. In a private US claims database, the cumulative re-operation rate was 14.5% after a median 9 years of follow-up²⁷, with sling revision/removal at 3.7%²⁸. Other small studies in non-US populations have shown low rates of long-term complications (1-3%)²⁹. A recent UK study among 95,057 women and a median follow-up time of 5.5 years found that risk of re-operation was 2.6% at 1 year, 5.5% at 5 years, and 6.9% at 9 years³⁰. More specifically, mesh removal rates were 3.3% at 9 years in this population. Another UK study among 92,246 patients with first time mesh implantations for SUI found a 5-year complication rate of 9.8%³¹. A Canadian study of 59,887 women found ~3.5% may require mesh removal or revision within 10 years of initial surgery³².

There have also been some systematic reviews and meta-analyses done attempting to further understand the complications in this population. In 2015, a systematic review of studies with a follow-up of 36 months for TOMUS and 60 months for RPMUS were searched and studies comparing the two were

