4. STUDY DESIGN

This project will be a multi-site retrospective cohort analysis of trans-vaginally placed synthetic midurethral slings (MUS) implanted in patients for the indication of stress urinary incontinence for mid- and long-term outcomes (1 year and greater). We will identify all patients at each of the sites that have received a MUS through administrative and device implantation data. The key exposures will be MUS devices identified by administrative codes. Because ascertainment of the surgical approach is critical to the evaluation of post-operative complications, and has differing rates depending on the approach, we will determine which approach was used: Retropubic MUS (RPMUS), Transobturator MUS (TOMUS), Single-Incision Sling (SIMUS), or Adjustable Sling (AMUS). In prior work at Mayo, determination of the surgical approach was present in 100% of cases in the operative notes. We will also identify all patients that received a surgery for SUI without mesh (autologous or cadaveric fascial sling or burch colposuspension or bulking agents) and evaluate the same outcomes of interest in that population separately to provide an indirect comparison group. No direct comparison of mesh and non-mesh groups will be conducted. Patients with concomitant surgeries at the time of trans-vaginal mesh implantation for SUI will be included. The primary outcomes of interest are long-term safety outcomes relevant to these devices and defined in Section 7. In addition, using the Mayo Clinic data, we will be able to validate the electronic data with the manually curated data from 2010-2012². We will leverage this data to better understand how much of the data can be electronically generated and where additional information would need to be collected in an electronic environment.

Beyond the variables collected for exposures, outcomes, and cohort inclusion/exclusion, important covariates relevant to the device exposures and outcomes, and present prior to the surgery, will also be collected.

These include:

- Patient demographics
- Chronic pain
- Prior abdominal surgery
- Receipt of urodynamic testing (structured data will not have the results)
- BMI
- Insurance payer

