Insertion of mesh or other prosthesis for repair of pelvic floor defect 57267

General Prolapse Repair codes:

Repair of cystocele and rectocele, no graft 70.50 Repair of cystocele, no graft 70.51 Repair of rectocele, no graft 70.52 Other operations on cul-de-sac (repair of vaginal enterocele), no graft 70.92 Vaginal construction, no graft 70.61 Vaginal reconstruction, no graft 70.62 Vaginal suspension and fixation, no graft 70.77 Colpocleisis 70.80 Other uterine suspension 69.22 Vaginal repair of chronic inversion of uterus 69.23 Other repair of uterus and supporting structures 69.29 Other operation on supporting structure of the uterus 69.98 Obliteration of vaginal vault and total excision of vagina 70.4

General Prolapse CPT-4 Codes:

Rectocele repair 45560 Anterior colporrhaphy, repair of cystocele 57240 Posterior colporrhaphy, repair of rectocele 57250 Combined anteroposterior colporrhaphy with enterocele repair 57265 Combined anteroposterior colporrhaphy 57260 Synthetic Mid-Urethral Slings for Stress Urinary Incontinence in Women Protocol 1 Enterocele Repair—vaginal approach 57268 Enterocele Repair — abdominal approach 57270 Colpocleisis 57120 Colpopexy, vaginal, extraperitoneal approach 57282 Colpopexy, vaginal, intraperitoneal approach 57283 Insertion of mesh; vaginal approach 57267 Pereyra procedure, including anterior colporrhaphy 57289 Removal or revision of sling for SUI 57287 Revision (including removal) of prosthetic vaginal graft; vaginal approach 57295 Sling operation for SUI 57288 Uterine suspension 58400 Uterine suspension 58410 Vaginal hysterectomy, with repair of enterocele 58270 Vaginal hysterectomy, with colpourethrocystopexy, complicated 58293 Vaginal hysterectomy with repair of enterocele, complicated 58294

Sling Codes:

Retropubic Urethral Suspension 59.4, 59.71, 59.79 *Must be used concurrently with other prolapse repair codes.

International Classification of Diseases (ICD)-9/10 Diagnosis and Procedure Codes ⁵⁶

Diagnoses

Urinary incontinence	625.6/N39.3 Stress urinary incontinence, female
	599.82/N36.42 Intrinsic sphincter deficiency
	788.30/R32 Urinary incontinence, unspecified
	788.31/N39.41 Urge incontinence
	788.32/N39.3 Stress urinary incontinence, male
	788.33/N39.46Mixed incontinence (male) (female)
	788.34/N39.42 Incontinence without sensory awareness
	788.35/N39.43Post-void dribbling
	788.36/N39.44 Nocturnal enuresis
	788.37/N39.45 Continuous leakage
	788.38/N39.490 Overflow incontinence

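### CPT 57295 is flagged as a possible code for erosion surgery, but the mesh revision/removal outcome does not count it, so operations coded only that way would be missed

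*Protocol*

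**What the plan says.** Four places in the protocol bear on this.

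- **Section 7, Study Outcomes.** The first primary outcome is re-operation or mesh removal. Its definition has several components, the last of which is "or revision for mesh exposure".
- **Section 13, data-collection table, Re-Operation row.** The revision/removal part opens with "sling revision/removal-CPT codes 57287, 10120" and continues with ICD-10-PCS codes for removal or revision of a substitute in the urethra. 57295 is not among them.
- **Section 13, data-collection table, Mesh Removal row.** The definition begins "General, CPT 57287-Removal or revision of sling for stress incontinence (fascia or synthetic". In the same cell a starred note warns that "some erosions managed surgically may have been coded by a different CPT (i.e. 57295 revise vaginal graft via vaginal approach", and that these operations would then not carry 57287. No instruction follows.
- **Section 13, code lists reproduced from a prior study.** Among the general prolapse codes stands "Revision (including removal) of prosthetic vaginal graft; vaginal approach 57295". The list is given as an example and not as a study outcome definition.

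Section 4 also matters for the remedy: "Patients with concomitant surgeries at the time of trans-vaginal mesh implantation for SUI will be included".

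**The concern.** The written outcome is wider than the code list meant to find it. The protocol recognises that an operation belonging to the outcome may be recorded under another code, and it leaves that code outside the lists an analyst would program from.

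Mesh revision or removal is one of the safety results intended to inform regulatory decisions on these devices (Sections 3 and 10.2). The outcomes are analysed as time to event. A woman whose only revision carries 57295 would therefore stay event-free, or would receive a later event date if she has another qualifying operation afterwards. An omission of this kind can only lose true sling events.

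**Working it through.** **Is the code counted anywhere?** The protocol states no sample size or expected event count for this outcome, so there is no figure of its own to reproduce. The first check is of the text.

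1. The Re-Operation row's revision/removal codes are 57287, 10120 and urethral ICD-10-PCS codes. 57295 is absent.
2. The erosion and exposure diagnosis codes in that row are listed as subtypes of a revision/removal re-operation. They classify an operation already found by a procedure code; they do not identify a new one.
3. The Mesh Removal row lists 57287 and mentions 57295 only as a caveat.
4. The separate Mesh Erosion outcome rests mainly on diagnosis codes. It may flag the erosion, but it does not record a removal or revision operation.
5. Chart review covers 50 to 100 cases per site (Section 6), with no stated enrichment for events. At a 3.3% removal rate that gives 50 × 0.033 = 1.65 to 100 × 0.033 = 3.3 expected events per site, too few to measure the share coded 57295.

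Nothing in the protocol therefore recovers an operation coded only as 57295.

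**How large could the loss be?** Inputs from Section 1.1:

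- 1.6% of women having sling surgery had erosion needing intervention (New York study)
- 3.3% mesh removal at 9 years (UK study)
- 6.9% re-operation at 9 years (same UK study)

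Assumption: a share *f* of erosion interventions is coded only as 57295. The protocol does not give *f*; 10% to 30% is used to show a range.

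Loss in percentage points = 1.6 × *f*. Relative loss = (1.6 × *f*) / reference rate. The synopsis gives sling counts for three sites that sum to 6,106 + 5,413 + 887 = 12,406. Women missed = 12,406 × 0.016 × *f*.

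| *f* (assumed) | Points lost | Share of 3.3% removal | Share of 6.9% re-operation | Women missed per 12,406 |
|---|---|---|---|---|
| 10% | 0.16 | 4.8% | 2.3% | about 20 |
| 20% | 0.32 | 9.7% | 4.6% | about 40 |
| 30% | 0.48 | 14.5% | 7.0% | about 60 |

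Both denominators are shown because Section 3 names revision or removal as an outcome in its own right, while Section 7 combines it with repeat incontinence surgery.

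**The case against.** The best reply is that 57295 is not excluded. It stands inside the definition cell of the Mesh Removal outcome, directly after 57287, and a programmer could take the starred note as a prompt to include it. The table reads as a working document: the same row offers possible options, and other rows contain open questions. Final code sets may sit in a data dictionary that is not shown. Parts of the Re-Operation cell were also damaged in text extraction.

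Part of this stands. The defect is an unresolved note, not a decision to leave the code out. It does not remove the point, because the opening line of the revision/removal list is intact without 57295, and a note that can be read either way does not fix a primary outcome.

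A second reply is that 57295 describes revision of a prosthetic vaginal graft and is listed with prolapse codes. Since women with concomitant surgery are included, adding it without a condition would count some prolapse-graft revisions as sling events. That is correct, and it shapes the fix. A check limited to prolapse mesh at or before the index operation would not be enough, because such mesh can also be placed during follow-up.

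A third reply is that some of these operations may also carry 57287, 10120 or a urethral PCS code and so be found anyway. That limits the size but not the direction.

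**Conclusion.** The point holds as an inconsistency between the stated outcome and its code lists. Operations coded only as 57295 would be missed, and the revision/removal rate would be too low by whatever share they make up.

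The protocol does not fix the size. The 0.16 to 0.48 points rest on an assumed share of 10% to 30% and on no co-coding under a listed code. The relative losses combine a New York erosion rate with UK nine-year rates, so they are illustrations and not estimates.

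Three stronger readings are tempting and are not supported:

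- **That under-capture is established.** The note says only that some operations may have been coded this way.
- **That the whole re-operation outcome is affected.** Revision of exposed mesh is one component of one of the three primary outcomes in Section 7, and against the 6.9% re-operation rate the illustrative loss is about half as large as against the 3.3% removal rate.
- **That differing coding habits will appear as site differences.** The protocol says nothing about how the use of 57295 varies between sites.

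The change should be made, since the outcome serves a regulatory purpose and the correction is small.

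**What to change.** - Add 57295 to the revision/removal list in the Re-Operation row and to the Mesh Removal row, and replace the starred note with that rule.
- Count it for women with no prolapse-mesh code (for example CPT 57267 or ICD-9 procedure codes 70.53 to 70.55, already listed in the appendix) at any time up to the date of the 57295 procedure, including after the index surgery.
- For women with such a code, report 57295 procedures separately.
- Show the revision/removal rate with and without 57295.

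The cost is one more code in the extraction, one look-back check and one sensitivity row. The downside is a small residual risk of counting a prolapse-graft revision when the prolapse mesh was placed outside the site and is not in its records. Showing the rate both ways makes the possible effect of that visible.
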